**Details on C-SSRS Mapping**

Columbia-Classification Algorithm of Suicide Assessment (C-CASA)

**Table 1. C-CASA Suicidality Events and Codes**

| Event Code | Event   |
|------------|---|
| 1          | Completed suicide                                   |
| 2          | Suicide attempt                                     |
| 3          | Preparatory acts towards imminent suicidal behavior |
| 4          | Suicidal ideation                                   |
| 5          | Self-injurious behavior, intent unknown             |
| 6          | Not enough information, fatal                       |
| 7          | Self-injurious behavior, no suicidal intent         |
| 8          | Other, accident, psychiatric; mental                |
| 9          | Not enough information, non fatal                   |

\* Note: Event Codes 5, 6, 8 and 9 are not applicable to prospectively collected data

**Table 2. C-SSRS Mapped to C-CASA - Suicidality Events and Codes**

| C-CASA Event Code | C-CASA Event                                 | C-SSRS Response   |
|--------------------------|---|--|
| 1                        | Completed suicide                                   | As captured in the safety database   |
| 2                        | Suicide attempt                                     | “Yes” on “Actual Attempt”  |
| 3                        | Preparatory acts towards imminent suicidal behavior | “Yes” on any of the following: 
 
• “Aborted attempt”, or
 
• “Interrupted attempt”, or
 
• “Preparatory Acts or Behavior”
 
  |
| 4                        | Suicidal ideation                                   | “Yes” on any of the following: 
 
• “Wish to be dead”, or
 
• “Non-Specific Active Suicidal Thoughts”, or
 
• “Active Suicidal Ideation with Any Methods (Not Plan) without Intent to Act”, or
 
• “Active Suicidal Ideation with Some Intent to Act, without Specific Plan”, or
 
• “Active Suicidal Ideation with Specific Plan and Intent”
 
 |
| 7                        | Self-injurious behavior, no suicidal intent         | “Yes” on “Has subject engaged in Non-suicidal Self-Injurious Behavior?”  |

#### Appendix 4. Sample SAS Code for Estimand 1

```
libname c3941002 "/Volumes/app/..... /data_vai" ;
```

```
data ps;
```

```
    set c3941002.adps;
```

```
run;
```

```
data look;
```

```
    set ps;
```

```
    where param = "EASI02-Total Sum" and viswin ne .;
```

```
    keep subjid param paramn avisit age sex trta viswin visit xviswin aval base chg pchg trtan;
```

```
run;
```

```
**example data for a single visit;
```

```
**created from systemic study ;
```

```
**ignore values, only used for illustration;
```

```
**data already has one record per subject per visit even if
```

```
**data is missing. Proc Mi needs missing values in order to impute;
```

```
data ex1;
```

```
    set look;
```

```
      where upcase(avisit)='WEEK 6';  
regimen = "QD";  
if trtan = 1 then dose=0;  
if trtan = 2 then dose=0.01;  
      keep subjid dose regimen chg aval base;  
  
run;  
  
proc means data=ex1;  
      class regimen dose;  
      var chg aval;  
  
run;  
  
proc sort data=ex1 out=ex2;  
      *data must be sorted by regimen before usin proc mi;  
      by regimen dose;  
  
run;  
  
*imputing aval=observed so range of endpoint 0-72 can be included in;  
  
*mi procedure;  
  
proc mi data=ex2 seed=1022 nimpute=1000 out=outimp max=72 min=0;  
      by regimen;  
      class dose;
```

```
monotone reg(aval= base/details);  
mnar model( aval/modelobs = (dose="0"));  
var base aval;
```

```
run;
```

```
proc univariate data=outimp;
```

```
var aval;
```

```
histogram ;
```

```
run;
```

```
data outimp1;
```

```
set outimp;
```

```
chg = aval - base;**calculate chg from baseline
```

```
run;
```

```
proc sort data = outimp1 out = outimp2;
```

```
by _imputation_ regimen dose subjid;
```

```
run;
```

```
proc mixed data=outimp2;
```

```
by _imputation_ ;  
class dose regimen;  
model chg = base dose*regimen;  
lsmeans dose*regimen/ diff alpha=.1 ;  
ods output diffs=diffs lsmeans=lsmeans;
```

**run;**

**data** diffnout;

```
set diffs;  
  
**only keep within regimen contrasts vs placebo;  
where regimen = _regimen and dose = 0;
```

**run;**

```
**now use mianalyze on lsmean differences;  
  
**First sort by group, regimen and _dose (dose = 0 for all groups);
```

**proc sort** data=diffnout out=diffnout1;

```
by regimen _dose _imputation_;
```

**run;**

```
**now mianalyze by regimen and _dose;  
  
**NB mianalyze only uses estimates and standard errors not CI limits etc.;  
  
proc mianalyze data=diffsout1 alpha=.1; **specify alpha for 90% CIs here;  
  
  by regimen _dose;  
  
  modeleffects estimate;  
  
  stderr stderr;  
  
  ods output parameterestimates=parameterestimates;  
  
run;
```

**Appendix 5. Sample SAS Code for Estimand 2 – Risk Difference using Chan and Zhang (1999)**

```
PROC BINOMIAL DATA=<DATASET> GAMMA=0 ALPHA=<Value>;
```

```
PD/EX ONE STD;
```

```
PO <POPULATION VARIABLE>;
```

```
OU <OUTCOME VARIABLE>;
```

```
RUN;
```

**Appendix 6. Sample SAS Code for the Confidence Interval of a Binomial Proportion (Blyth-Still-Casella)**

```
PROC BINOMIAL DATA=<DATASET> ALPHA=<value>;
```

```
BI/BS;
```

```
OU <RESPONSE VARIABLE>;
```

```
RUN;
```

### Appendix 7. Sample SAS Code for MMRM

```
proc mixed data=_dsnin order=internal alpha=0.1;
  by PARAMN;
  class SUBJID AVISITN TRTPN;
  model PCHG = BASE TRTPN AVISITN TRTPN*AVISITN /solution ddfm=kr;
  repeated AVISITN/ subject =SUBJID type=un r rcorr; /**try UN first, if not converged, will use CS***/
  lsmeans TRTPN*AVISITN / diff cl alpha=0.1;
  ods output lsmeans=lsmeans diffs=diffs;

run;

/*For one-sided P-value calculation, the LOWER tail side should be used. */;
```

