### **5.2.2. Analyses for Continuous Endpoints**

Landmark (cross-sectional) analysis of key continuous endpoints will use analysis of covariance (ANCOVA). The ANCOVA model will include terms for treatment arm and baseline score of the dependent variable. Least-squares means at the mean overall baseline score will be presented along with 90% confidence intervals.

Mixed model repeated measures (MMRM) models will be used. The fixed effects of treatment, visit, and treatment by visit interaction will be included. Visit will be modeled as a categorical covariate. Unstructured covariance matrix will be assumed for the model errors. Compound symmetry covariance matrix will be used if the model with unstructured covariance doesn't converge.

When modeling the change from baseline values, the variable for visit will start with the first post-baseline visit, and the actual baseline value will be included as a covariate. At each visit, estimates of least square mean (LSM) values and the LSM differences between the PF-07038124 treated group and the corresponding vehicle group will be derived from the model for AD and Psoriasis patients separately. The corresponding p-values and 90% confidence intervals will also be derived from the model.

Unless stated otherwise, descriptive summary statistics for all continuous variables will be presented on mITT observed data by treatment group and will include n, mean, median, standard deviation, minimum and maximum.

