##### 6.1.1.1. Main Analysis

- Estimand strategy: Primary Estimand ([Section 2.1.1](#)). This estimand is intended to provide an estimate of the treatment effect in the absence of prohibited medication use in a population that may or may not be fully compliant with the treatment.
- Analysis set: mITT ([Section 4](#)) using data prepared in the description of the full analysis set.
- Analysis methodology: Percent change from baseline will be analyzed using an ANCOVA with the observed (or imputed) Week 6 change from baseline EASI score as the dependent variable with treatment arm and baseline EASI score as the independent variables. Same method will be used for change from baseline PASI score at Week 6.
- Intercurrent events and missing data: Data prohibited medication will be excluded and set to missing. Missing data which will be multiply imputed using a control-based strategy as described in ([Section 5.3](#)). A thousand (1000) imputed datasets will be used in the analysis and results combined using PROC MIANALYZE.
- The least-squares (LS) means, the 90% confidence interval for the LS means, the difference between the LS means for each pair of treatment groups, and the corresponding 90% confidence interval will be presented.

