###### Supplementary Analyses:

- Mixed model repeated measures (MMRM) models will be used (assuming missing data are missing at random). The fixed effects of treatment, visit, and treatment by visit interaction will be included. Visit will be modeled as a categorical covariate.

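### The MMRM fits one baseline slope for all visits; for absolute change in PASI or EASI this can cost precision at later visits, and a baseline-by-visit term would remove the restriction

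*SAP*

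**What the plan says.** SAP 6.1.1.2 describes the MMRM thus: "The fixed effects of treatment, visit, and treatment by visit interaction will be included". SAP 5.2.2 lists the same terms and brings baseline in once: "the actual baseline value will be included as a covariate". The model statement in Appendix 7 agrees with the text: "model PCHG = BASE TRTPN AVISITN TRTPN*AVISITN". Text and code therefore match: treatment may differ by visit, the baseline slope may not.

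The covariance is unstructured, with compound symmetry as the fallback. SAP 5.2.2 reports this model visit by visit ("At each visit, estimates of least square mean (LSM) values and the LSM differences"), with p-values and 90% intervals.

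The MMRM is a supporting analysis. SAP 6.1.1.2 places it under supplementary analyses and states that it assumes data missing at random; SAP Appendix 1 calls it a sensitivity analysis, for percent change in EASI and absolute change in PASI. The primary analysis in SAP 6.1.1.1 is a Week 6 ANCOVA with "treatment arm and baseline EASI score as the independent variables" and control-based multiple imputation, and the same method is applied to PASI. For the other continuous secondary endpoints, SAP 6.2.3.1 names ANCOVA at Week 6 only.

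**The concern.** Suppose lesions shrink roughly in proportion, so that the score at visit t is r_t times baseline. Absolute change is then -(1 - r_t) times baseline. Its slope on baseline is shallow early and steeper once more disease has cleared. A single slope cannot follow this, and the part of the baseline effect it misses stays in the residual.

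Two things are at stake for absolute change. First, later-visit estimates may be less precise than the data allow, with only 12 evaluable per arm planned in psoriasis. Second, the MMRM is the missing-at-random comparison for the primary result. The primary ANCOVA fits its own Week 6 slope, while the MMRM takes a slope shared with Weeks 1 to 4. A Week 6 difference between the two would then mix the missing-data assumption with a difference in baseline adjustment.

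**Working it through.** **The plan's own figures.** The documents give no figure for MMRM precision, so the check starts from the sample size.
- AD (protocol 9.2.1): SE = 48 × √(2/21) = 14.81; 50/14.81 = 3.38; normal power at two-sided 0.05 is 92.2%, and 90.9% by noncentral t. Stated: about 90%.
- Psoriasis (protocol 9.2.2): SE = 4.2 × √(2/12) = 1.71; 4.5/1.71 = 2.62; normal power at two-sided 0.10 is 83.6%, and 81.5% by noncentral t. Stated: about 80%.
- Dropout: 21/0.75 = 28 and 12/0.75 = 16 per arm, as stated.

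These inputs reproduce and are carried forward.

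**Inputs from the documents.** 28 and 16 randomized per arm, 25% dropout, SDs of 48 (EASI percent change) and 4.2 (PASI change), four post-baseline treatment visits (Weeks 1, 2, 4, 6), unstructured covariance.

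**Assumed inputs.** Baseline SD, slope at each visit, residual SDs, and a residual correlation of 0.75 between adjacent visits that decays with lag. Dropout is monotone and unrelated to outcome. Both arms share the same slope, no treatment effect is set, and randomization is not stratified.

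**Method.** 1,500 simulated trials per scenario. Each is fitted by REML with the SAP model and again with BASE*AVISITN added. The table gives the empirical SD of the treatment difference under the common slope divided by that under baseline-by-visit. Above 1 means the common slope is less precise.

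| Scenario | Wk 1 | Wk 2 | Wk 4 | Wk 6 |
|---|---|---|---|---|
| EASI % change, slope 0 throughout | 1.000 | 0.992 | 0.993 | 0.989 |
| EASI % change, slope 0 to -3 points per EASI point | 1.004 | 0.996 | 1.000 | 1.007 |
| PASI change, baseline SD 3, slope -0.1 to -0.5, Week 6 residual SD 3.9 | 1.004 | 0.994 | 0.996 | 1.022 |
| PASI change, baseline SD 3, slope -0.1 to -0.7, Week 6 residual SD 3.0 | 1.010 | 1.013 | 1.075 | 1.129 |
| PASI change, baseline SD 5, slope -0.1 to -0.7, Week 6 residual SD 2.3 | 1.032 | 1.084 | 1.359 | 1.549 |

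The third row is tied to the protocol's SD: √((0.5 × 3)² + 3.9²) = 4.18. The fourth totals √((0.7 × 3)² + 3.0²) = 3.66, somewhat below 4.2. The fifth totals √((0.7 × 5)² + 2.3²) = 4.19, but baseline then explains (0.7 × 5)²/4.19² = 70% of the Week 6 variance. It marks an extreme, not an expectation.

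**Rough hand check.** If the common slope settles near the Week 1 value of -0.1, where variance is smallest, the unmodelled Week 6 slope is -0.4 in the moderate case and -0.6 in the steeper case. The Week 6 residual SD grows by √(3.9² + (0.4 × 3)²)/3.9 = 1.046 and √(3.0² + (0.6 × 3)²)/3.0 = 1.166. The simulated 1.022 and 1.129 are smaller but of the same order, as expected once the extra parameters are paid for.

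**Why percent change differs.** Under proportional clearing, percent change is -100(1 - r_t) whatever the baseline. The slope is zero at every visit and the extra term has nothing to gain.

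**Corroboration.** A separate simulation of absolute change (400 trials per setting, slopes -0.1 to -0.5) gave baseline-by-visit to common-slope SD ratios at Week 6 of 0.989 and 0.977 for baseline SD 3 (16 and 28 per arm), and 0.923 and 0.916 for baseline SD 4. With a constant slope the ratios were 1.008 and 1.010, and the cost in model-based SE was about 1-2%.

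**Bias.** Under the SAP model the mean treatment difference stayed at zero within simulation error in every scenario.

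**The case against.** A single baseline covariate is a legitimate specification, Appendix 7 is labelled sample code, and formal inference rests on the Week 6 ANCOVA. The slopes and baseline SDs are assumptions; no section of either document says the relation steepens. Stratification by severity and the entry limits (EASI 3 to 21; psoriasis BSA 5% to 15%) hold down baseline imbalance. Three more parameters beside an unstructured covariance with 16 per arm is a trade-off. The MMRM and the primary ANCOVA already differ by design in how they treat missing data. All of this stands, and it makes the point minor.

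It does not remove the point. The second difference from the ANCOVA, in baseline adjustment, serves no purpose. For absolute change the trade is also lopsided: about 1-2% lost if the slope is constant, against about 2% to 13% gained at Week 6 in the moderate and steeper cases.

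A reader might infer that visit-level estimates lose precision in general. The documents do not support that. The Appendix 7 line models percent change, which is the AD primary variable and the form of three of the five continuous secondary endpoints in SAP 6.2.3. A reader might also infer that the MMRM is the only inferential model at Weeks 1, 2 and 4. That cannot be settled: protocol 9.4.1 and 9.4.2 apply the primary-estimand analysis to other continuous endpoints at the scheduled visits, SAP 5.3.1 mentions landmark analyses by week, and part of SAP 6.2.3 is redacted.

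**Conclusion.** The point holds for absolute change from baseline only, as an optional improvement. The MMRM constrains the baseline slope to be equal at all visits, in both text and code. For PASI change the Week 6 standard error is about 2% larger in the moderate case and about 13% larger with a steeper slope. Week 4 ranges from none to about 7%, and Weeks 1 and 2 show little or no loss. Secondary EASI change follows by the same mechanism. For percent change the difference is about -1% to +1%.

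These sizes depend on assumed slopes, baseline SDs, residual SDs and correlation, and on simulated trials without stratification. The real loss is unknown until baseline data are seen. It would be wrong to conclude that the treatment estimate is biased or that the primary result or sample size is affected: no bias appeared, and the primary ANCOVA fits its own Week 6 slope.

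**What to change.** Add BASE*AVISITN to the model statement in SAP Appendix 7, and name baseline-by-visit among the fixed effects in SAP 5.2.2 and 6.1.1.2, at least for absolute change in PASI and EASI. If the single slope is kept, say why. No new data are needed. The cost is three more fixed-effect parameters (four visit-specific slopes in place of one) and about 1-2% in standard error if the slope is in fact constant. The existing compound-symmetry fallback can stay as written.

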### Appendix 8. List of Abbreviations

The following is a list of abbreviations that may be used in the protocol.

| Abbreviation | Term                              |
|--------------|-----------------------------------|
| AA           | alopecia areata                   |
| Ab           | antibody                          |
| Abs          | absolute                          |
| AD           | atopic dermatitis                 |
| AE           | adverse event                     |
| ALT          | alanine aminotransferase          |
| AST          | aspartate aminotransferase        |
| CCI          | [REDACTED]                        |
| CCI          | [REDACTED]                        |
| BCG          | bacille Calmette-Guerin           |
| β-hCG        | beta-human chorionic gonadotropin |
| BID          | twice daily                       |
| BMI          | body mass index                   |
| BP           | blood pressure                    |
| BSA          | body surface area                 |
| BUN          | blood urea nitrogen               |
| CAT          | computerized axial tomography     |
| CC           | [REDACTED]                        |
| CD           | Crohn's disease                   |
| CFR          | Code of Federal Regulations       |

| Abbreviation     | Term  |
|------------------|---|
| CIOMS            | Council for International Organizations of Medical Sciences |
| CK               | creatinine kinase   |
| CKD-EPI          | Chronic Kidney Disease Epidemiology Collaboration           |
| CC               | [REDACTED]  |
| CLIA             | Clinical Laboratory Improvement Amendments                  |
| CCI              | [REDACTED]  |
| CMV              | Cytomegalovirus   |
| CO 2  | carbon dioxide (bicarbonate)                                |
| CONSORT          | Consolidated Standards of Reporting Trials                  |
| CRF              | case report form  |
| CRO              | contract research organization                              |
| CSR              | clinical study report                                       |
| C-SSRS           | Columbia suicide severity rating scale                      |
| CT               | clinical trial  |
| DILI             | drug-induced liver injury                                   |
| CCI              | [REDACTED]  |
| [REDACTED]       | [REDACTED]  |
| DU               | dispensable unit  |
| EASI             | Eczema Area and Severity Index                              |
| EBV              | Epstein Barr virus  |
| EC 50 | Half-maximal effective concentration                        |
| EC               | ethics committee  |
| ECG              | Electrocardiogram   |
| eCRF             | electronic case report form                                 |
| E-DMC            | external data monitoring committee                          |
| EDP              | exposure during pregnancy                                   |
| eGFR             | estimated glomerular filtration rate                        |
| EMA              | European Medicines Agency                                   |
| EOS              | end of study  |

| Abbreviation | Term   |
|---------------------|---|
| EOT                 | end of treatment                                    |
| ePRO                | electronic patient reported outcome                 |
| ET                  | early termination                                   |
| EU                  | European Union                                      |
| EudraCT             | European Clinical Trials Database                   |
| F                   | bioavailability                                     |
| FDA                 | Federal Drug Administration                         |
| FSH                 | follicle-stimulating hormone                        |
| Fu                  | fraction unbound                                    |
| GCP                 | Good Clinical Practice                              |
| GGT                 | gamma-glutamyl transferase                          |
| HBcAb               | hepatitis B core antibody                           |
| HBsAb               | hepatitis B surface antibody                        |
| HBsAg               | hepatitis B surface antigen                         |
| HBV                 | hepatitis B virus                                   |
| HCVAb               | hepatitis C virus antibody                          |
| HIPAA               | Health Insurance Portability and Accountability Act |
| HIV                 | human immunodeficiency virus                        |
| HRT                 | hormone replacement therapy                         |
| hsCRP               | high sensitivity C-reactive protein                 |
| IB                  | investigator's brochure                             |
| IC 50    | half-maximal inhibitory concentration               |
| ICD                 | informed consent document                           |
| ICH                 | International Council for Harmonisation             |
| ID                  | identification                                      |
| IFN- $\alpha$       | Interferon alpha                                    |
| IGA                 | Investigator's Global Assessment                    |
| IgE                 | immunoglobulin E                                    |
| IgG                 | immunoglobulin G                                    |

| Abbreviation | Term                               |
|---------------------|---|
| IGRA                | Interferon Gamma Release Assay            |
| IL-                 | interleukin                               |
| IND                 | investigational new drug application      |
| INR                 | international normalized ratio            |
| IP                  | investigational product                   |
| IP-10               | interferon-induced protein 10             |
| IP manual           | investigational product manual            |
| IRB                 | institutional review board                |
| IRC                 | internal review committee                 |
| IRT                 | interactive response technology           |
| IUD                 | intrauterine device                       |
| IUS                 | intrauterine hormone-releasing system     |
| IV                  | intravenous                               |
| IWR                 | interactive Web-based response            |
| LFT                 | liver function test                       |
| LLOQ                | lower limit of quantification             |
| JAK                 | Janus Kinase                              |
| LDL                 | low density lipoprotein                   |
| MAD                 | multiple ascending dose                   |
| MCH                 | mean corpuscular hemoglobin               |
| MCHC                | mean corpuscular hemoglobin concentration |
| MCV                 | mean corpuscular volume                   |
| Mg                  | milligram                                 |
| MMP12               | Matrix metalloproteinase 12               |
| mRNA                | messenger ribonucleic acid                |
| MRI                 | magnetic resonance imaging                |
| Msec                | millisecond                               |
| MTX                 | methotrexate                              |
| N/A                 | not applicable                            |

| Abbreviation | Term  |
|---------------------|--|
| NOAEL               | no-observed-adverse-effect level                       |
| NRS                 | Numerical Rating Scale                                 |
| NTIS                | Night time itch scale                                  |
| PASI                | Psoriasis area and severity index                      |
| PCD                 | primary completion date                                |
| PCP                 | primary care physician                                 |
| PCR                 | polymerase chain reaction                              |
| PD                  | pharmacodynamic(s)                                     |
| PG                  | polypropylene glycol                                   |
| CCI                 | [REDACTED]   |
| [REDACTED]          | [REDACTED]   |
| PI                  | principal investigator                                 |
| PK                  | pharmacokinetic(s)                                     |
| CCI                 | [REDACTED]   |
| PPD                 | Purified Protein Derivative                            |
| PP-NRS              | Peak Pruritus Numerical Rating Scale                   |
| PR                  | pulse rate   |
| PRO                 | Patient reported outcomes                              |
| PSAAD               | Pruritus and Symptoms Assessment for Atopic Dermatitis |
| PT                  | prothrombin time                                       |
| PVC                 | premature ventricular contraction/complex              |
| QD                  | once daily   |
| QFT-G               | QuantiFERON-TB Gold Test                               |
| QFT-GIT             | QuantiFERON-TB Gold In-tube Test                       |
| QT                  | Q wave interval  |
| QTc                 | corrected QT   |
| QTcF                | corrected QT (Fridericia method)                       |
| Qual                | qualitative  |
| QW                  | once a week  |

| Abbreviation | Term  |
|--------------|---|
| RBC          | red blood cell                                |
| CCI          |   |
| SAD          | single ascending dose                         |
| SAE          | serious adverse event                         |
| SAP          | statistical analysis plan                     |
| SCr          | serum creatinine                              |
| S Cystatin C | serum Cystatin C                              |
| SoA          | schedule of activities                        |
| SOP          | standard operating procedure                  |
| SRSD         | single reference safety document              |
| SSID         | subject study identification n                |
| SToD         | study team on demand                          |
| SUSAR        | suspected unexpected serious adverse reaction |
| C            |   |
| CI           |   |
| TB           | tuberculosis                                  |
| TBili        | total bilirubin                               |
| TdP          | Torsade de Pointes                            |
| TEAE         | treatment emergent adverse events             |
| CCI          |   |
| TNF          | tumor necrosis factor                         |
| TYK2         | Tyrosine Kinase 2                             |
| UC           | ulcerative colitis                            |
| ULN          | upper limit of normal                         |
| US           | United States                                 |
| UVA          | ultraviolet A light                           |
| UVB          | ultraviolet B light                           |
| VZV          | varicella zoster virus                        |
| WBC          | white blood cell                              |

| Abbreviation | Term                     |
|---------------------|---------------------------------|
| WOCBP               | woman of childbearing potential |
